2.1.4 Safety endpoints

The safety analysis will be based on the reported AEs and other safety information, such as clinical laboratory data and vital signs.

Observation period

The observation period will be divided into 3 periods:

- Pre-treatment period is defined from the signed informed consent up to the first dose of double-blind IMP injection.
- Treatment Emergent Adverse Event (TEAE) period is defined as the time from the first dose of double-blind IMP injection to the last dose of IMP injection + 70 days (10 weeks) as residual effect of treatment is expected until 10 weeks after the stop of double-blind IMP. As the hour of IMP injection is not collected, the time of double blind IMP injection refers, here and in the rest of the document, to the date of double-blind IMP injection.

The TEAE period will include:

- The efficacy treatment period defined as the time from the first dose of double-blind IMP injection up to the day of last dose of double-blind IMP injection + 21 days, as serum concentration of alirocumab >10 µg/mL is expected for approximately 21 days following administration of 150 mg, and because throughout the previous studies it was observed that when alirocumab concentrations declined below this concentration, decrease in effect on LDL-C is observed.
- The residual efficacy treatment defined as the time from the day of last dose of double-blind IMP injection + 22 days up to the day of last dose of double-blind IMP injection + 70 days (10 weeks).
- Post-treatment period is defined as the time starting the day after the end of the TEAE period up to resolution/stabilization of all serious adverse events (SAE) and AEs of special interest (AESI), whichever comes last.

The on-study observation period is defined as the time from the day of the first dose of double-blind IMP injection until the last protocol planned visit of the patient (Week 32 phone call).

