The incidence of premature treatment discontinuation (irrespective of the reason) and premature treatment discontinuation due to AEs will be presented graphically by treatment group on randomized and treated patients (as randomized), using Kaplan-Meier method.

The incidence of premature study discontinuation (irrespective of the reason) and premature study discontinuation due to AEs will be presented graphically by treatment group on randomized and treated patients (as randomized), using Kaplan-Meier method.

Patients with insufficient post-treatment follow-up will be described on the safety population by treatment group. A patient is considered with insufficient post-treatment follow-up or without post-treatment follow-up at the end of the study in the following cases:

- If the patient is not assessed at the post-treatment follow-up call or any post-treatment visit, unless patient died before, or
- If the last post-treatment visit is less than 9 weeks after the last double-blind injection.

All major deviations potentially impacting efficacy analyses, randomization, and drug-dispensing irregularities, and other major or critical deviations will be summarized in tables giving numbers and percentages of deviations by treatment group. Patients excluded from the ITT/mITT population will be listed as well as patients with major deviations potentially impacting efficacy analyses not resulting in exclusion from ITT/mITT population. These deviations are listed in the data review and surveillance plan.

Additionally, the following analysis populations will be summarized by treatment group:

- Randomized population;
- Efficacy population: ITT population and mITT;
- Safety population;
- [REDACTED]
- ADA population.

Definitions of the study populations are provided in [Section 2.3](#).

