- Number of patients experiencing TEAEs by primary SOC and PT, sorted by the internationally agreed SOC order and by decreasing incidence of PTs within each SOC (in the alirocumab group). This order will be applied to all other TEAEs tables by SOC and PT, unless otherwise specified;

- All TEAEs by treatment group regardless of relationship in one column and, in the same table, in a second column, related to IMP according to investigator's opinion by primary SOC, HLT, HLT and PT;
- All TEAEs by maximal intensity (ie, mild, moderate or severe), presented by primary SOC and PT, sorted by the sorting order defined above;
- The event rate per patient-year (the number of patients with an event in question divided by total patient-years) will be provided for all TEAEs by SOC and PT. For a patient with event, patient year is censored at time of first event; for patient without event, it corresponds to length of TEAE period;
- Kaplan-Meier curves will be provided, when appropriate, for time from first dose of double-blind IMP to the first occurrence of selected TEAEs as well as incidence rates at the time of analysis (Week 24 for the first step analysis, Week 32 for the final analysis). Hazard ratio versus placebo group and corresponding 95% CI will be given. Patients without any event will be censored at the end of the TEAE period. Selected TEAEs will be local injection site reactions, general allergic reactions, neurocognitive events, hepatic disorder events and TEAE related to any clinically significant signal that needs further characterization;

Analysis of all treatment emergent serious adverse event(s)

- All serious TEAEs by primary SOC, HLT, HLT, and PT.
- All serious TEAEs by treatment group regardless of relationship in one column and, in the same table, in a second column, related to IMP according to investigator's opinion, by primary SOC, HLT, HLT, and PT;
- The event rate per patient-year will be provided for all serious TEAEs by SOC and PT;
- All SAEs will be listed.

Analysis of all treatment-emergent adverse event(s) leading to treatment discontinuation

All TEAEs leading to treatment discontinuation, by primary SOC, HLT, HLT, and PT.

Analysis of groupings of adverse events including selected adverse events of special interest

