2.5.3 Missing data

For categorical variables, patients with missing data are not included in calculations of percentages unless otherwise specified. When relevant, the number of patients with missing data is presented.

Handling of baseline definition if time of first double-blind administration or time of assessment at Week 0 visit is missing

If the time of the first double-blind administration or time of assessment at Week 0 visit is missing then the baseline value is defined as the last available value obtained before (ie, at an unscheduled visit) or on the day of the first double-blind IMP administration.

Handling of computation of treatment duration if investigational medicinal product first or end of treatment date is missing

If the last or first injection date is missing, the exposure duration and compliance will be left as missing.

Handling of safety and efficacy analysis periods and survival analysis if investigational medicinal product end of treatment date is missing

If the last injection date is missing, then this date is imputed to the earliest between:

- The last day of the month and year, when applicable or else the 31st of December of the year;
- The date of the end of treatment visit (Week 24 visit for completer, early end of treatment visit for patients who prematurely discontinued the IMP);
- And the date of the last contact;

for the purpose of safety and efficacy analysis period start and/or end.

Handling of medication missing/partial dates

No imputation of medication start/end dates or times will be performed. If a medication date or time is missing or partially missing and it cannot be determined whether it was taken prior or concomitantly, it will be considered a prior, concomitant, and post-treatment medication.

Handling of adverse events with missing or partial date/time of onset

Missing or partial AE dates and times will be imputed so that if the partial AE date/time information does not indicate that the AE started prior to treatment or after the TEAE period, the AE will be classified as treatment-emergent. These data imputations are for categorization purpose only and will not be used in listings. No imputation is planned for date/time of AE resolution.

Handling of adverse events when date and time of first investigational medicinal product administration is missing

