3 INTERIM ANALYSIS

No formal interim analysis for efficacy is planned since analysis of primary and key secondary efficacy endpoints will be final at the time of first-step analysis described below. All efficacy data will be available for final analysis at a cut-off date corresponding to the Week 24 visit of the last patient, and both the efficacy and safety analyses will be performed in a first-step analysis. Since safety data are collected until the end of the study (Week 32), an update of the safety analysis will be performed in a second-step analysis at the end of the study.

The first-step analysis will be conducted as soon as all patients have been randomized and have at least all their data up to Week 24 analysis window collected and validated. It will consist of a final analysis of the primary and secondary efficacy endpoints up to Week 24, as well as safety analysis performed on all safety data collected up to the common cut-off date, defined as the date of the last Week 24 visit.

The second-step analysis will be conducted at the end of the study and will consist in the updated analysis of safety endpoints until Week 32. No multiplicity adjustment for multiple analyses is needed because all efficacy analyses will be completed at the time of the first-step analysis. Selected individuals who are not involved in the conduct of the study after the first step analysis will perform the second step analysis; individual patient identification will not be released to anyone who is directly involved in the ongoing conduct of the study.

Analyses methods and conventions described in the other sections of this SAP will be applied for all analyses as applicable. The following additional rules will apply for analyses performed at first step analysis:

- Any lipid assessments within analysis windows up to Week 24 will be taken into account (may include few unscheduled lipid data soon after the cut-off date).
- Patients without end of treatment visit performed at the time of the cut-off date will be considered as ongoing and exposed up to the cut-off date. Therefore:
 - Patients who did not complete treatment period nor prematurely discontinued the study treatment at cut-off date will be analyzed as “ongoing” in the disposition summary;
 - Their TEAE period, treatment period and on-study observation period will end at the cut-off date;
 - Their treatment duration will be derived by considering date of cut-off as last injection date and last capsule date.

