- Analyses of number of injections, mean injection frequency, percentage of days with under/above-planned dosing and compliance (for injections and capsules) will be performed up to the last injection and capsule reported in the e-CRF up to the cut-off date.
- AEs occurring, worsening or becoming serious after the cut-off date will not be included in the analyses. However, any available outcome before database lock, regardless of timing in relation to the cut-off date, of an AE starting prior to the cut-off date will be taken into account. Medications, treatment discontinuations/completions, and deaths occurring after the cut-off date will not be included in the analyses.

- Post-treatment period, post-study period are not applicable for ongoing patients. Analyses of post-treatment AEs, post-study deaths, and post-treatment medications will be performed for patients who either completed or prematurely discontinued the treatment before or at the cut-off date.
- Analysis of status at last study contact and proportion of patients with insufficient follow-up will be provided for patients who either completed or prematurely discontinued the treatment before or at the cut-off date.

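### Adverse-event at-risk time runs to last dose + 70 days even when observation stopped earlier, so patient-year rates come out slightly too low

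*SAP*

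**What the plan says.** SAP 2.4.6.1 plans event rates per patient-year for all TEAEs and all serious TEAEs by SOC and PT. A patient with the event contributes time up to the first event; "for patient without event, it corresponds to length of TEAE period". For the Kaplan-Meier curves and hazard ratios of selected TEAEs, the rule is "Patients without any event will be censored at the end of the TEAE period". Protocol 11.4.3.1 has the same censoring rule.

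SAP 2.1.4 defines the TEAE period as first double-blind injection to 70 days after the last one. Neither document ends it earlier for death, withdrawal or loss to follow-up.

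SAP section 3 sets the first-step cut-off at the date of the last Week 24 visit and adds three relevant rules:

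- "Patients without end of treatment visit performed at the time of the cut-off date will be considered as ongoing"
- for those patients only, "Their TEAE period, treatment period and on-study observation period will end at the cut-off date"
- for everyone, "AEs occurring, worsening or becoming serious after the cut-off date will not be included in the analyses"

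The SAP expects some follow-up to be incomplete. Section 2.2 describes patients with insufficient post-treatment follow-up, one criterion being "If the last post-treatment visit is less than 9 weeks after the last double-blind injection". That classification is not used to shorten at-risk time.

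**The concern.** A rate is only interpretable if its numerator and denominator cover the same time. Here they can differ in two ways.

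1. **First step only.** Events after the cut-off are dropped for all patients, but the TEAE period is cut there only for those without an end-of-treatment visit. Because the cut-off is the last Week 24 visit, nearly everyone has had that visit and falls outside the cap. Patients whose Week 24 visit came shortly before the cut-off keep time in which no event can be counted.
2. **Both steps.** A patient who dies, withdraws fully or is lost before last dose + 70 days is treated as observed and event-free to that date. Protocol 10.3.4 asks for at least 10 weeks of follow-up after early stopping, so this concerns only patients in whom that fails.

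Both push the rates down. Safety is a primary objective, and protocol 6.3 says a Week 24 analysis would serve scientific communication, so the first-step rates may be the ones reported first.

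**Working it through.** **Timeline.** The last planned injection is at Week 22, which is Day 1 + 22×7 = Day 155. Adding 70 days gives Day 225, which matches the protocol flow chart's Week 32 contact. The Week 24 visit is Day 169. The largest overrun for a completer is 225 − 169 = 56 days, or 56/225 = 25% of that patient's period.

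**First step.** The documents give no accrual pattern, so assume the time from Week 24 visit to cut-off is uniform over 0 to A days. A patient is affected if that time is under 56 days.

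- Share affected = 56/A
- Mean excess over all patients = 56²/(2A)
- Understatement for an uncommon event ≈ mean excess/225

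| A (days) | Share affected | Mean excess (days) | Understatement |
|---|---|---|---|
| 180 | 31% | 3136/360 = 8.71 | 3.9% |
| 365 | 15% | 3136/730 = 4.30 | 1.9% |
| 540 | 10% | 3136/1080 = 2.90 | 1.3% |

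Clustering in 90 days would give 3136/180 = 17.42 days, or 7.7%. For commoner events the effect is a little smaller: with a constant true rate of 0.20 per patient-year, the reported rate would be about 0.193, 0.196 or 0.198 for 6, 12 or 18 months.

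**First-step Kaplan-Meier.** Take a constant hazard with 10% incidence by Day 169. For completers, everything up to the Week 24 visit precedes the cut-off, so the Week 24 estimate is 10.0% under either rule. At Day 225 the correct value is 1 − 0.9^(225/169) = 13.1%. As written with A = 180, 69% of patients are observed for all 56 further days (event probability 0.0343) and 31% for part of them (average 0.0173). The estimate is 0.10 + 0.9×(0.689×0.0343 + 0.311×0.0173) = 12.6%.

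**Final analysis.** Suppose a share p is lost, with last dose uniform over the 12 injections (mean Day 78, so the counted period ends on average at Day 148) and last contact uniform over the next 70 days (mean excess 35 days). Then understatement ≈ 35p / [225(1 − p) + 148p].

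- p = 2%: 0.70/223.46 = 0.3%
- p = 5%: 1.75/221.15 = 0.8%
- p = 10%: 3.50/217.30 = 1.6%
- p = 15%: 5.25/213.45 = 2.5%

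Simulation under the same assumptions gives 0.32%, 0.80%, 1.64% and 2.50%. Week 32 Kaplan-Meier for the event above is 13.06% as written against 13.10% capped (2% lost), and 12.83% against 13.14% (15% lost).

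A deliberately high case has 15% lost on the day of a Day 78 last dose. Counted time is 0.85×225 + 0.15×148 = 213.45 days; observed time is 0.85×225 + 0.15×78 = 202.95 days; understatement is 10.5/213.45 = 4.9%.

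The ±7-day window on the Week 32 call (protocol section 10) adds a little. If calls are uniform over Days 218 to 232, half fall before Day 225 by 3.5 days on average, giving 1.75/225 = 0.8%.

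**A contrast within the SAP.** For laboratory and vital-sign PCSAs, SAP 2.4.6.3 and 2.4.6.4 censor event-free patients at the last assessment actually made in the TEAE period. The adverse-event rule does not follow that principle.

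**The case against.** The strongest objection is about weight. Safety is descriptive. With 333 alirocumab patients, a 10% event gives about 33 cases and a Poisson relative standard error of 1/√33 ≈ 17%; a 2% event gives about 7 cases and roughly 38%. A shift of 1% to 4% would not change a safety conclusion. The first-step part is temporary, and it alters at-risk time for only 10% to 31% of patients under the 6- to 18-month assumptions. Uniform accrual is also doubtful, since Type 1 recruitment may outlast Type 2 and safety is tabulated by diabetes type as well as pooled. The 7.7% and 4.9% figures need unlikely conditions. All of this stands, and it limits the point to a small one.

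It can also be argued that section 3 restricts first-step safety data to those collected by the cut-off, so a cap might be implied for everyone. But the cap is written for one named group. A programmer following the text would not apply it to the rest.

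A third argument is that AEs can be reported retrospectively, so time after the last formal contact is not wholly unobserved, and a contact date extended by an event report would make follow-up depend on outcome. That is a fair warning about how the cap is defined, and the fix below allows for it. It does not justify counting a dead or lost patient as observed to last dose + 70 days.

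**Conclusion.** The rule is wrong as written, and its effect is small. Patient-year rates are understated, never overstated. At the first step the size is about 1.3% to 3.9% for Week 24 visits spread evenly over 18 to 6 months. In the final analysis it is about 0.3% to 2.5% for 2% to 15% lost. The extremes of 7.7% and 4.9% are bounds under clustered visits and very early loss, not expectations. Accrual, death and loss figures are assumptions, because the documents give none.

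The n (%) tables do not change. The first-step gap affects only the Kaplan-Meier curve after Week 24 and disappears at the Week 32 update. Hazard ratios move little if loss is similar between arms, and no bias between arms is claimed.

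**What to change.** In SAP 2.4.6.1, end at-risk time for both patient-years and Kaplan-Meier censoring at the earliest of: last dose + 70 days, death, last contact with AE information and, at the first step, the cut-off date. In SAP section 3, apply the cut-off cap to all patients rather than only those considered ongoing. Define the contact date as the last visit or call at which AEs were asked about, so that a late event report does not itself extend follow-up.

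Protocol 11.4.3.1 has the same censoring rule, so record the change in SAP 1.5.

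The cost is one minimum in the derivation, two SAP sentences, a short definition and one line in 1.5. A last-contact date is already used in SAP 2.5.3 ("And the date of the last contact"), though only to impute a missing last injection date, so the AE-specific version has to be specified. Reported rates will be slightly higher.

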In the placebo-controlled and ezetimibe-controlled pooled studies, no dose relationship was noted for any adverse events (AEs) and there was no evidence of a pattern in the type of AEs observed. The percentages of patients who experienced at least 1 treatment-emergent adverse event (TEAE), at least 1 treatment-emergent serious adverse event (SAE) and any TEAEs leading to permanent treatment discontinuation were similar between the alirocumab and control groups.

There was no safety signal observed with neurologic events and neurocognitive disorders, ALT increase and hepatic disorders, adjudicated CV events, diabetes mellitus, and ophthalmologic disorders in the alirocumab-treated group overall, but more cataracts (2.1%) were noted in patients treated with alirocumab who achieved 2 consecutive LDL-C values <25 mg/dL compared to those treated with alirocumab who did not meet this criterion (0.6%).

The most common adverse reactions in patients treated with alirocumab were local injection site reactions (6.2% patients in the alirocumab group versus 4.2% in control groups in the global pool). Injection site reactions, influenza and pruritus were identified as adverse drug reactions (ADRs). Rare and sometimes serious allergic adverse reactions (eg, hypersensitivity, eczema nummular, urticaria, and hypersensitivity vasculitis) have been reported from clinical studies in patients receiving alirocumab.

The analysis of the safety data with Q2W dosing did not suggest a safety signal as of 31 December 2014.

Overall, the safety profile of the alirocumab Q4W dosing regimen was similar to alirocumab Q2W regimen, except for the frequency and onset of injection site reactions. The reactions tended to occur sooner after the first drug injection, and last longer, in the alirocumab group.

Further details on alirocumab are provided in the Investigator's Brochure.

Rationale for this study

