- All grouping of TEAEs including AESI as listed in [Section 2.1.4.1](#) will be analyzed using selections defined in [Section 2.1.4.1](#). They will be presented by SMQ and PT (when selection is based on SMQs) or by SOC and PT (when selection is based on the e-CRF tick box or HLT/HLT). The summaries will be sorted by decreasing incidence of PT within each SOC/SMQ (in the alirocumab group).
- Overview of each AESI and grouping of hepatic disorder events will be presented, summarizing number (%) of patients with any
 - AE;
 - TEAE;
 - TEAE leading to death;
 - TEAE leading to permanent treatment discontinuation.

- In addition, the following variables will be tabulated for the local injection site reactions TEAEs:
 - Highest intensity of the event (mild, moderate, severe);
 - Mean duration;
 - Number of events divided by the number of double-blind IMP injections received;
 - Time from first double-blind IMP injection to first injection site reaction;
 - Number of double-blind IMP injections up to the first injection site reaction;
 - Description of the highest intensity of each symptom recorded in the specific e-CRF page with tables.
- Besides, description of symptoms and possible etiologies for general allergic reaction TEAE reported by investigator, will be presented.

Analysis of pre-treatment and post-treatment adverse events

- All pre-treatment AEs by primary SOC and PT, sorted by the internationally agreed SOC order and decreasing incidence of PTs (in the alirocumab group) within each SOC;
- All pre-treatment AEs leading to treatment discontinuation by primary SOC and PT, sorted by the sorting order defined above;
- All post-treatment AEs by primary SOC and PT, sorted by the internationally agreed SOC order and decreasing incidence of PTs (in the alirocumab group) within each SOC;
- All post-treatment SAEs by primary SOC and PT, sorted by the sorting order defined above.

Subgroup of patients with 2 consecutive LDL-C <25 mg/dL

- If applicable, similar summaries of TEAEs as those described previously will be also provided on the safety subgroup population of patients with 2 consecutive results of calculated LDL-C <25 mg/dL. Only TEAE for which it will be confirmed or unclear that they occurred, worsened or became serious the day or after the first level of calculated LDL-C <25 mg/dL will be considered.

Analysis of non-serious treatment emergent adverse events

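### SAP 2.4.6.1: in the subgroup with two consecutive LDL-C values below 25 mg/dL, events count from the first such value but patient-years, by default, run from first dose, so event rates come out too low

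*SAP*

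**What the plan says.** The subgroup paragraph of SAP 2.4.6.1 states that, if applicable, "similar summaries of TEAEs as those described previously will be also provided on the safety subgroup population" of patients with two consecutive calculated LDL-C results below 25 mg/dL. It then restricts the numerator to events that "occurred, worsened or became serious the day or after the first level of calculated LDL-C <25 mg/dL will be considered". An event qualifies if it is "confirmed or unclear that they occurred" (or worsened, or became serious) in that window, so doubtful timing counts in.

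The summaries being inherited appear earlier in the same section. Most are number (%) tables. Two are rates per patient-year, for all TEAEs and for serious TEAEs. A patient with an event is censored at the first event; "for patient without event, it corresponds to length of TEAE period". SAP 2.1.4 opens the TEAE period at the first double-blind injection and closes it 70 days after the last. Kaplan-Meier curves, produced when appropriate, use "time from first dose of double-blind IMP to the first occurrence of selected TEAEs", with a hazard ratio against placebo.

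The subgroup paragraph gives no time origin of its own and names no comparator.

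Protocol section 4 shows why the subgroup is of interest: "more cataracts (2.1%) were noted in patients treated with alirocumab who achieved 2 consecutive LDL-C values <25 mg/dL", against 0.6% in alirocumab patients who did not meet that criterion.

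**The concern.** A rate is interpretable only if the time in the denominator is time in which an event could enter the numerator. Here the numerator opens at the first LDL-C below 25 mg/dL, while the only available definition of patient-years opens at first dose. The first scheduled post-baseline lipid sample is at Week 8, so on the planned schedule each subgroup member brings about eight weeks or more that add to the denominator and almost nothing to the numerator. This is immortal-time dilution, and it makes very low LDL-C look safer than the data show.

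At stake is the reading of one descriptive table about an exposure for which the protocol itself reports an imbalance. LDL-C is masked to sites after randomization, so the exposure is examined at analysis. A second, smaller issue is comparison: the cataract contrast in the protocol was made within alirocumab, and the SAP does not plan a table for the other side of it.

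**Working it through.** The documents give no rate or size for this subgroup, so there is no plan figure to reproduce. The timeline can be checked: the last injection at Week 22 is Day 1 + 22 × 7 = Day 155, and 155 + 70 = Day 225, the flow chart's target day for Week 32.

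**Inputs**
- TEAE period for a patient completing treatment: Day 1 to Day 225, or 224 elapsed days (SAP 2.1.4; last dose from the protocol synopsis).
- Scheduled post-baseline lipid panels: Weeks 8, 12, 20 and 24, Days 57, 85, 141 and 169 (protocol 1.2). Week 20 is the last scheduled visit at which a first value below 25 can still be followed by a second.

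**Patient-year rate.** With the first value below 25 on day *d*, the share of patient-years before counting opens is (*d* − 1)/224. For rare events, the rate as written divided by the rate with aligned time is 1 minus that share.

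| First value below 25 | Share before counting opens | Rate rises, once aligned, by |
|---|---|---|
| Week 8 | 56/224 = 25.0% | 224/168 = ×1.33 |
| Week 12 | 84/224 = 37.5% | 224/140 = ×1.60 |
| Week 20 | 140/224 = 62.5% | 224/84 = ×2.67 |

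Counting days inclusively (225 in all) gives 24.9%, 37.3% and 62.2%. The ±3-day window at Week 8 (Days 54 to 60) moves the first share between 53/224 = 23.7% and 59/224 = 26.3%. For a patient whose follow-up is cut at Day 169 in the first-step analysis, the shares are 56/168 = 33%, 84/168 = 50% and 140/168 = 83%.

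**A mix of crossing times.** The documents give none. Assume 60%, 20% and 20% at Weeks 8, 12 and 20, and a true rate of 3.0 per 100 patient-years. Mean time after the threshold is 0.6 × 168 + 0.2 × 140 + 0.2 × 84 = 145.6 days, and 145.6/224 = 0.65. The SAP default would report about 3.0 × 0.65 = 1.95; simulation gave 1.94, and 3.00 with aligned time. For frequent events (50 per 100 patient-years) the simulated ratio was 0.63.

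**Kaplan-Meier.** If everyone crosses at Week 8, the curve is only shifted: the Week 32 estimate is 1 − exp(−0.03 × 168/365.25) = 1.37%, the same as the 24-week estimate from the threshold. With the 60/20/20 mix it is 1.19% against 1.37%.

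**Number (%) tables.** These have no time denominator, so the time origin does not alter them. They do cover a shorter window than the all-alirocumab column.

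**Comparator.** Entry requires a screening LDL-C of at least 70 mg/dL. Falling from 70 to below 25 needs a drop of more than 1 − 25/70 = 64%, while protocol section 4 gives placebo changes of 0.5 to 4.2%. The placebo side should be nearly empty.

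**Scale.** The subgroup size is not given. Assuming 10% to 50% of the 333 alirocumab patients (33 to 166) and the 2.1% cataract frequency, 0.7 to 3.5 cataracts are expected, with a probability of none between 0.979^33 = 50% and 0.979^166 = 3%.

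**The case against.** The strongest reply is that the SAP asks only for similar summaries and never says the subgroup clock starts at first dose; a careful programmer might align it. That is fair as far as it goes. The first-dose origin is the default reading and not an express subgroup rule. But the section contains one definition of patient-years, and silence leaves it in force.

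Several stronger inferences are tempting and are not supported:
- **That crude percentages carry the same fault.** They do not; only the window differs, and the SAP plans no side-by-side reading with the all-alirocumab column.
- **That Kaplan-Meier estimates are understated to the same degree.** They are affected less, and not at all at Week 32 if all cross at Week 8. Cataract is not a named Kaplan-Meier event and would enter only as a declared signal.
- **That no event in the first eight weeks can ever count.** Events of unclear timing are kept, earlier events that later worsen or become serious count, and unscheduled samples may supply an earlier value. The unclear-timing rule pushes the numerator up.
- **That very low LDL-C is the only exposure with a reported imbalance, or this table the only check on cataract.** Protocol section 4 also reports injection site reactions at 6.2% against 4.2%, and notes no ophthalmologic signal in alirocumab patients overall. Cataract still appears as a preferred term in the main tables.

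It is also fair that the Week 20 figure is an edge case. Up-titration is reserved for patients at 70 mg/dL or above at Week 8, so patients already low then have no later dose increase to bring about a late first crossing. Finally, the summaries test no hypothesis, and the dates needed to recalculate are collected anyway. This limits the consequence; it does not justify the denominator.

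**Conclusion.** The point holds for the rates per patient-year, for all TEAEs and for serious TEAEs. Read as written, they are too low for this subgroup. For a patient completing treatment, about 25%, 37% or 62% of patient-years cannot yield an event of known post-threshold timing, for a first value below 25 at Week 8, 12 or 20. This rests on the planned visit schedule, a last dose at Week 22, rare events at a constant rate, and the default reading of the time origin. The overall shortfall depends on a distribution of crossing times that the documents do not give.

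The severity is minor: the analysis is descriptive and conditional, and few cataracts are expected. The missing within-alirocumab comparator is a limit on interpretation, not an error, and a comparison of groups defined after baseline would remain non-randomized.

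The SAP already shows the right instinct elsewhere. In its general safety rules (2.4.6), the analysis by up-titration status separates the time before Week 12 to reduce bias and counts events from a common later start.

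**What to change.** Add to the subgroup paragraph of SAP 2.4.6.1: in this subgroup, patient-years, and Kaplan-Meier time where curves are produced, start on the date of the first calculated LDL-C below 25 mg/dL; alternatively, keep the first-dose time scale with delayed entry at that date. State in a table footnote that the number (%) tables cover a shorter window than the all-alirocumab column.

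Optional and descriptive: show alirocumab patients who do not meet the criterion, with a matched start of follow-up, and list the cataract preferred terms for both groups. Use a common landmark or time-varying LDL-C status. Starting one group at its first value below 25 and the other at Week 8 would bring in a new mismatch. Membership also needs a second low value later on, which a landmark or time-varying definition handles more cleanly.

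The cost is SAP wording and one derivation, plus one column if the option is taken; no new data are needed. The price is less person-time, hence less precise and probably less favourable subgroup rates.
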